6.5 Prior Anti-Cancer History

Prior anti-cancer therapies classified as systemic therapy (including chemotherapy, immunotherapy, and targeted therapy), radiotherapy, surgery, or “Other” are to be recorded on the Prior Anti-neoplastic Therapy eCRF page during screening. The number of lines of prior anti-cancer therapies and therapy class will be tabulated. The number of lines of prior anti-cancer

therapies will also be summarized by descriptive statistics. The number of lines will be calculated based on the following:

A regimen (i.e. unique regimen number) would count as a line of therapy if

- (therapy class = systemic therapy) AND (treatment setting = [metastatic disease / palliative OR unresectable locally advanced disease / palliative])

or

- (therapy class = systemic therapy) AND (treatment setting = primary / neoadjuvant / adjuvant / curative) AND (date of detection of metastatic disease <= 6 months after [cancer therapy end date in this regimen])

Prior anti-cancer therapies will also be listed for FAS patients.

6.6 Inclusion and Exclusion Criteria

Treated and non-treated patients who did not meet inclusion or exclusion criteria will be listed separately for the All Patients Set.

7 Treatments and Medications

7.1 Prior and Concomitant Medications

Prior and concomitant medications will be documented at screening and updated during the study.

Prior and concomitant medications will be coded using the WHO Drug Dictionary Enhanced Version WHODDRUG Dec16 WHO-DDE B2.

A prior medication is defined as a medication where both the start and end dates are before the date of the initial C1D1 IMCnyeso dose received.

A concomitant medication is defined as one where the end date is either on or after C1D1 date or is missing. The start date of a concomitant medication can be before or after C1D1 date. For a medication with partial or completely missing onset date, unless it can be determined to be “prior to the first infusion” from the incomplete start date or end date (e.g., month, year is before C1D date, or end date is before C1D1 date), the medication will always be assumed to be concomitant. Medications initiated prior to the start of study treatment and continued after the start of study treatment will be counted as both prior and concomitant medications.

For the purpose of categorizing medications as prior or concomitant, incomplete medication start and stop dates will be imputed as follows:

Missing start dates (where UK and UKN indicate unknown or missing day and month respectively):

- UK-MMM-YYYY: Assume 01-MMM-YYYY. If the month and year are the same as the first dose of study drug month and year, then assume the date of first dose of study drug.
- UK-UKN-YYYY: If the year is prior to the year of first dose of study drug, assume 01-JAN-YYYY of the collected year. If the year is the same as the first dose of study drug year, then assume the date of first dose of study drug.

Missing stop dates for concomitant medications data will be handled as follows (where UK, UKN and UNKN indicate unknown or missing day, month, and year respectively).

- UK-MMM-YYYY: Assume the last day of the month.
- UK-UKN-YYYY: Assume 31-DEC-YYYY.
- UK-UKN- UNKN: Assume ongoing and leave it missing.

A listing for both prior and concomitant medications will be created for all FAS patients.

7.2 Study Treatments

7.2.1 Extent of Exposure

Total number of cycles, expected dose, actual dose and duration in months of treatment for IMCnyeso, as well as the dose intensity (total actual dose received/actual duration), the relative dose intensity (the dose intensity as percentage of planned dose/planned duration), number of doses beyond progression, number of doses beyond progression and the actual dose beyond progression will be summarized by descriptive statistics for the SAF.

- The treatment period will begin with the first treatment on Day 1 in the first cycle (C1D1). For the purpose of treatment scheduling, a cycle consists of 4 weeks (28 days). The total number of cycles of study drug received will include also partial cycles and reduced dose cycles.
- The duration is defined as the number of months from the date of the initial C1D1 IMCnyeso dose received to the last date of IMCnyeso dose received as recorded on EX dataset plus the protocol defined post-dose rest (i.e. 1 day).

Duration of Treatment (months) = (date of last dose - the date of first dose + 1) / 30.4375.

- Because study drug reduction may occur during the study, the exposure to study drug will also be characterized by total actual dose received, which is defined as the sum of the actual dose levels during the study.
- Dose intensity is the total actual dose received divided by duration of treatment in weeks.

$$\text{Dose Intensity (mcg/wk)} = \frac{\text{Sum of Actual Doses}}{\text{Duration of Treatment}}$$

- The relative dose intensity (%) is 100 x (total actual drug given until treatment discontinuation) / (expected amount of drug given until treatment discontinuation). If there is a difference between the last dose date and the treatment discontinuation date (i.e. the date the *decision* was made to stop treatment), then date of last dose would be used.
- The actual dose beyond progression is defined as the total actual dose taken by the patient after the progression according to RECIST v1.1. Patients who did not progress, will not be included in this calculation. The summary of number of doses taken beyond progression and corresponding time duration (months) will be provided.

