6.2 Treatment Regimen and In-Patient Hospitalization

Patients enrolled in this study will receive treatment with single-agent IMCnyeso dosed weekly on Days 1, 8, 15, and 22 of each 4-week cycle. All dosages prescribed and dispensed to patients and all dose changes during the study must be recorded on the Dosage Administration Record and electronic case report form (eCRF).

For each administration of study medication, a physician must be present at the site or immediately available to respond to emergencies. Study sites will be instructed on the conservative management of symptoms associated with CRS (eg, hypotension), as described in [Section 6.15](#). Fully functional resuscitation equipment and medications to handle acute infusion-related emergencies (eg, anaphylaxis, CRS) must be available at each study site.

Patients will be hospitalized for 2 nights following the administration of the first dose (C1D1) of IMCnyeso and will remain at the site for overnight observation following administration of the second dose (C1D8). In addition, patients receiving intra-patient escalation (IPE) will be hospitalized overnight following the first three doses (C1D1, C1D8, and C1D15). After reviewing safety, PK, and cytokine data from at least 3 patients enrolled at a given dose level, the SST may decide that 1 night of hospitalization is adequate after the first dose for subsequent

patients (with longer hospitalization if indicated). After Phase I is completed and the SST has reviewed all available relevant data for at least 6 patients at the RP2D, the SST may decide to reduce the minimum required monitoring time during the Phase II portion of the study to no less than 8 hours post-end of infusion on C1D1, C1D8, and/or C1D15 (with longer hospitalization if clinically indicated). Patients who experience certain AEs may require additional in-patient monitoring as described in [Section 6.15](#).

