7.2 Treatment Period Schedule

The treatment period starts with Day 1 of Cycle 1 (C1D1). A treatment cycle is defined as 28 days for the purposes of scheduling procedures and evaluations.

Any assessments required on C1D1 that are also performed as part of Screening do not need to be repeated on C1D1 if the data were obtained 72 hours prior to the first dose of study treatment. For subsequent visits, pregnancy testing may be performed up to 72 hours prior to dosing and other safety assessments may be performed up to 24 hours prior to dosing.

During the study visits, all tests and/or procedures should occur on schedule whenever possible. A visit window of ± 7 days (with a minimum of 7 days between doses of IMCnyeso) is allowed unless otherwise indicated in the protocol. If study drug infusions are delayed, the assessments associated with those infusions should be rescheduled accordingly. However, the timing of protocol-specified radiological assessments should be calculated in weeks using C1D1 as reference and should not be adjusted because of delays in treatment.

Assessments required during the treatment period are presented by visit in [Table 7-2](#). For patients receiving IPE, follow the alternate Cycle 1 schedule provided in [Section 13.4](#). Assessments marked “X” should be performed prior to dosing. Assessments that are to be performed at multiple timepoints are marked with the number of timepoints (including optional timepoints, if applicable) for the visit (eg, 2 \times is twice) and details of the timepoints are provided in the footnote. Additional details regarding the assessments are provided in [Section 7.4](#). Please refer to [Section 6](#) for dosing details. Patients will continue treatment until they meet criteria for discontinuation, as described in [Section 6.16](#).

Table 7-2: Schedule of Treatment Period Assessments

Procedure	Cycle 1						Cycle 2				Cycle 3				Later Cycles			
Day of Cycle	1	2	8	9	15	22	1	8	15	22	1	8	15	22	Visits on Days 1, 8, 15, and 22			
Adverse events	X	X	X	X	X	X	X	X	X	X	X	X	X	X		X		
Concomitant medications	X	X	X	X	X	X	X	X	X	X	X	X	X	X		X		
Safety Assessments																		
Complete physical examination	X																	
Abbreviated physical examination			X		X	X	X	X	X	X	X	X	X	X		D1 of each cycle		
Weight	X						X				X						D1 of each cycle	
Vital signs	~14x	~14x		3x	3x	3x	3x	3x	3x	3x	3x	3x	3x	3x		3x each dosing day		
12-lead ECG (single)	2x						2x				2x					2x on C4D1, C5D1, and C6D1		

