9.4 Treatment Data

Actual dose and duration in days of treatment for IMCnyeso, as well as the dose intensity (actual dose received/actual duration) and relative dose intensity (the ratio of dose intensity to planned dose/planned duration) will be summarized by descriptive statistics by treatment group.

Concomitant medications and significant non-drug therapies prior to and after the start of the study treatment will be listed by patient and summarized by anatomical therapeutic chemical term and treatment group.

The reason for discontinuation from treatment will be summarized and listed, along with dates of first and last doses, duration of exposure to each study drug, and date of discontinuation for each patient.

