3.4 Dose Adjustment/Modifications

All doses administered to subsequent cohorts of patients will be determined by the SST and will be guided by the BLRM and will be subject to both the EWOC principle and the escalation rule. Dose-escalation decisions will be made by the SST, which will consist of the Study Investigators, the Sponsor Medical Monitor, and a Statistician. For each cohort, dose escalation or de-escalation decisions will be based on the SST's review of all relevant data available, from all dose levels evaluated in the ongoing study, including safety information, DLTs, all \geq Grade 2 toxicity data, PK, and pharmacodynamic data from evaluable patients (as defined in Section 6.10.2 of protocol version 4.0). The data and BLRM dose recommendations will be discussed and agreed upon during the dose-escalation teleconference (DETC), and all decisions will be documented in the meeting minutes and shared with all participating Principal Investigators.

The actual dose levels that have been tested in this study are shown in **Table 1** below. Actual doses will be determined using the BLRM and must be agreed upon by the SST.

Table 1 - IMCnyeso Dose Levels for Phase I Dose Escalation

Cohort number	Cohort description	IMCnyeso Dose(s) Tested	Enrollment (n)
1	3 mcg fixed dose	3 mcg	4
2	10 mcg fixed dose	10 mcg	3
3	30 mcg fixed dose	30 mcg	5
4	100 mcg fixed dose	100 mcg	3
5	30-100 mcg intra-patient dose escalation	30-100 mcg	5
6	30-100-180 mcg intra-patient dose escalation	30-100-180 mcg	4
7	30-100-300 mcg intra-patient dose escalation	30-100-300 mcg	6 (planned)

To better understand the safety, tolerability, and PK profile of single agent IMCnyeso, additional cohorts of patients may be enrolled at preceding dose levels or intermediate dose levels, before or in parallel, while proceeding with further dose escalation. The outcome from these cohorts will be included in the BLRM.

If the first 2 patients in a previously untested dose level experience a DLT, additional enrollment in that cohort will stop, the BLRM will be updated with this new information, and the SST will evaluate the available safety, PK, and pharmacodynamic data. By incorporating information gained at the preceding dose levels and provided the BLRM predicts that the risk of excessive toxicity remains below 25% (EWOC), additional patients may be enrolled at this dose level or a lower dose level as agreed upon by the SST.

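### SAP 7.2.1 ends treatment duration 1 day after the last weekly dose, citing a protocol rest that does not exist, so dose intensity in mcg/wk is overstated: 7-fold after 1 on-schedule dose, 27% after 4, 4% after 24

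*SAP*

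**What the plan says.** SAP 7.2.1 (Extent of Exposure) runs treatment duration from the first to the last dose "plus the protocol defined post-dose rest (i.e. 1 day"). Its formula is last dose date minus first dose date plus 1, divided by 30.4375 to give months. It then states: "Dose intensity is the total actual dose received divided by duration of treatment in weeks".

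Protocol 6.2 has IMCnyeso "dosed weekly on Days 1, 8, 15, and 22 of each 4-week cycle". Protocol 7.2 allows a visit window "with a minimum of 7 days between doses of IMCnyeso". Protocol 9.4 defines dose intensity only as actual dose over actual duration, without saying when duration ends.

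SAP 7.2.1 defines relative dose intensity twice. The opening sentence has "the relative dose intensity (the dose intensity as percentage of planned dose/planned duration"), which matches protocol 9.4: "relative dose intensity (the ratio of dose intensity to planned dose/planned duration"). A later bullet uses 100 times the ratio ("total actual drug given until treatment discontinuation) / (expected amount of drug given until treatment discontinuation"), with the last dose date used where it differs from the discontinuation date. SAP Section 12 lists no change from the protocol on any of this.

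**The concern.** The SAP credits its closing day to the protocol, but the protocol's dosing interval is 7 days and no 1-day rest appears in its text. The +1 is an ordinary inclusive day count. That is adequate for a duration in months, but it is the wrong denominator for a rate per week: n weekly doses are divided by about n - 1 weeks.

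The overstatement is largest for patients who stop early and fades with time on treatment. This has three consequences in the exposure table:

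- Values above the planned weekly dose appear although nobody was overdosed.
- Groups with different time on treatment cannot be compared.
- A missed dose can be nearly hidden in the absolute figure.

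The Phase I cohorts in SAP Table 1 have 3 to 6 patients, and SAP Section 4 reports mean and maximum as well as median, so one early stopper can dominate the summary. SAP 7.2.2 plans no compliance analysis, which leaves dose intensity and relative dose intensity as the main summaries of drug delivered against drug planned.

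**Working it through.** Neither document reports a dose intensity value, so there is no figure to reproduce. The check applies the SAP formula to the protocol schedule.

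**Inputs**

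- Dosing interval of 7 days, 4 doses per 28-day cycle (protocol 6.2 and 7.2).
- Duration in days = last - first + 1 (SAP 7.2.1). The SAP shows no conversion to weeks; days/7 is used here.
- Dose intensity = total actual dose / duration in weeks (SAP 7.2.1).
- Reference: each dose covers its 7-day interval, so duration = last - first + 7. This is inferred from the weekly schedule.

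**Formula**

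For n on-schedule doses, last - first = 7(n - 1) days. The SAP duration is 7n - 6 days and the reference duration is 7n days. The numerator is the same, so SAP / reference = 7n/(7n - 6), whatever the dose. With L = last - first + 1 in days, the ratio off schedule is (L + 6)/L.

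**100 mcg weekly, no missed dose** (reference 100 mcg/wk in every row)

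| Doses | SAP duration (days) | SAP dose intensity (mcg/wk) | Ratio |
|---|---|---|---|
| 1 | 1 | 100 × 7/1 = 700 | 7.00 |
| 2 | 8 | 200 × 7/8 = 175 | 1.75 |
| 4 | 22 | 400 × 7/22 = 127.3 | 1.273 |
| 8 | 50 | 800 × 7/50 = 112.0 | 1.12 |
| 12 | 78 | 1200 × 7/78 = 107.7 | 1.077 |
| 24 | 162 | 2400 × 7/162 = 103.7 | 1.037 |
| 52 | 358 | 5200 × 7/358 = 101.7 | 1.017 |

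**Step-up cohort** ("30-100-300 mcg intra-patient dose escalation", SAP Table 1), one full cycle: 30 + 100 + 300 + 300 = 730 mcg. SAP: 730 × 7/22 = 232.3 mcg/wk. Reference: 730/4 = 182.5 mcg/wk. The ratio is again 1.273.

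**Missed dose**, 100 mcg on Days 1, 8 and 22 only. SAP: 300 × 7/22 = 95.5 mcg/wk. Reference: 300/4 = 75 mcg/wk.

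**Delays** reduce the excess. Four doses with a total delay of 7, 14 or 21 days give 35/29 = 1.21, 42/36 = 1.17 and 49/43 = 1.14.

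**Alternative reading.** If the rest day were added on top of the inclusive day (+2 in all), the ratios after 1, 4 and 24 doses would be 7/2 = 3.5, 28/23 = 1.22 and 168/163 = 1.03. The SAP's explicit formula has +1 only.

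**Effect on a small cohort** (invented for illustration): one patient with 1 dose and three with 8 doses, all at 100 mcg weekly. Values are 700, 112, 112 and 112. The mean is 1036/4 = 259, the median 112 and the maximum 700 mcg/wk.

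**Relative dose intensity, Days 1, 8, 22 patient**

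- Later bullet: 300/400 = 75%.
- Opening sentence, 400 mcg planned over 28 days (100 mcg/wk): 95.45/100 = 95.5%.
- Opening sentence, 400 mcg planned over 22 days (127.27 mcg/wk): 95.45/127.27 = 75%.

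The two definitions agree if planned duration equals actual duration, and can disagree otherwise.

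**The case against.** The 7-day closing interval is not written in either document. Protocol 9.4 leaves the end of duration open, and the SAP's text and formula agree on +1. The same inclusive +1 is used for PFS, OS and ADA duration, so this could be seen as a house day-count convention with a wrong label, a choice of definition and not a miscalculation.

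The 7-fold figure needs a patient who received exactly one dose. Protocol 1.4 reports no adverse event leading to discontinuation among the first 15 patients, and the first on-treatment scan falls in Cycle 3, after about 8 doses, when the excess is 12%. Delays reduce it further.

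On relative dose intensity, the bullet can be read as the operative rule. Its use of the last dose date suggests the same window for actual and expected drug, and the example then gives 75% both ways. Exposure is also described by cycles, total dose and duration, and SAP 8.6 counts interruptions and reductions.

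Much of this stands. The closing interval is inferred, the large figures belong to early stoppers, and the consequence is confined to one descriptive table. But the inclusive day is harmless in a time-to-event duration, whereas in a per-week rate it puts a compliant patient above the planned weekly dose by an amount that depends on time on treatment. That is a wrong result from a stated rule, not only a wrong label. The single-window reading of relative dose intensity is plausible, but the section still carries two definitions and leaves planned duration undefined.

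**Conclusion.** The concern holds. The cited protocol rest is not in the published protocol text. Absolute dose intensity as defined is overstated 7-fold, by 27% and by 4% after 1, 4 and 24 doses. These sizes assume on-schedule weekly dosing and a 7-day interval after the last dose.

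The importance is low. Missed doses stay visible in the actual/expected ratio, which has no duration term and is not affected by the closing day. The absolute measure and the duplicate definition of relative dose intensity should still be corrected before the exposure table is programmed.

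**What to change.** In SAP 7.2.1:

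- Define dose intensity (mcg/wk) as total actual dose / ((last dose date - first dose date + 7)/7). A compliant 100 mcg weekly patient then shows 100 mcg/wk after any number of on-schedule doses.
- Delete the reference to a protocol-defined rest. The inclusive +1 may stay for first-to-last-dose duration in months.
- Keep one relative dose intensity: 100 × total actual dose / total expected dose over that same interval, with expected dose including the planned step doses in the intra-patient escalation cohorts. Delete the version based on planned dose over planned duration.

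In SAP Section 12, record the departure from protocol 9.4.

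The cost is one formula, one deleted phrase, one definition, one line in Section 12 and an update to the exposure program. No new data are needed, and nothing in treatment or dosing changes.

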6.15.2 IMCnyeso Dose Interruptions

One to two doses of IMCnyeso may be omitted to permit resolution of treatment-related toxicity. If a patient who misses more than 2 consecutive doses due to a treatment-related toxicity is experiencing clinical benefit, and in the opinion of the Investigator, the benefit/risk profile favors continued treatment, then treatment may be restarted after discussion with the Sponsor Medical Monitor. If more than 3 consecutive doses of IMCnyeso are not administered due to treatment-related toxicity or if a > 21-day treatment interruption occurs, the default position is that the patient must then permanently discontinue study treatment.

Patients whose treatment is interrupted or permanently discontinued due to an AE or clinically significant laboratory value must be followed up at least once a week (or more frequently if clinically indicated) for 4 weeks, and at approximately 4-week intervals thereafter, until resolution or stabilization of the event, whichever occurs first.

Table 6-4: Recommended Management and Dose Modifications by Toxicity Grade and Type

Grade	Recommended Toxicity Management	Dose Modifications
Cytokine Release Syndrome (occurring at least 1 hour after the start of infusion) - refer to modified grading system in Table 13-1		
Grade 1	
If not already hospitalized, admit for close observation (eg, monitor vital signs hourly); implement supportive care per institutional standards. Provide anti-pyretics and analgesics as needed; monitor fluid balance (IV fluid support as indicated). Consider prophylactic electrolyte supplementation for patients receiving IV fluids with low-normal serum phosphorus or magnesium.
 
Serum should be collected for central lab cytokine assessments (see Section 7.4.6.4).
	May continue dosing.

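### SAP 7.2.1 gives two formulas for relative dose intensity and ends the second at the last dose, so doses withheld for toxicity just before discontinuation leave the denominator

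*SAP*

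**What the plan says.** The opening paragraph of SAP 7.2.1 lists "the relative dose intensity (the dose intensity as percentage of planned dose/planned duration" among the exposure summaries. Protocol 9.4 has the same idea: "relative dose intensity (the ratio of dose intensity to planned dose/planned duration". Neither document defines planned duration, and treatment has no fixed length: under Protocol 3.5 it continues until discontinuation criteria are met.

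A later bullet in SAP 7.2.1 gives a second formula: "The relative dose intensity (%) is 100 x (total actual drug given until treatment discontinuation) / (expected amount of drug given until treatment discontinuation". It then adds an end-date rule: "If there is a difference between the last dose date and the treatment discontinuation date", "then date of last dose would be used". The SAP explains that the discontinuation date here means the date on which stopping was decided.

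Duration is "Duration of Treatment (months) = (date of last dose - the date of first dose + 1) / 30.4375", and dose intensity is the sum of actual doses divided by that duration in weeks.

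Treatment is "dosed weekly on Days 1, 8, 15, and 22 of each 4-week cycle" (Protocol 6.2). Protocol 6.15.2 lets one or two doses be omitted while a treatment-related toxicity resolves. It makes permanent discontinuation the default in either of two cases: "If more than 3 consecutive doses of IMCnyeso are not administered due to treatment-related toxicity", or an interruption of more than 21 days.

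SAP Section 12 reports no substantial change from the protocol. It names two added analysis sets and does not mention RDI.

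**The concern.** RDI is meant to show how much of the planned drug patients actually received. Under Protocol 6.15.2, toxicity can end treatment through a run of withheld doses followed by a decision to stop. All of those doses fall after the last administration. If the expected amount stops accruing at the last dose, that run has no effect on RDI, and the error can only raise RDI or leave it unchanged.

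There is also a question of reproducibility. Because planned duration is undefined, two programmers could both follow SAP 7.2.1 and produce different RDI columns. The duration formula adds a distortion of its own: a weekly regimen is charged one day rather than seven for its final dose, which inflates mcg/week most in patients with few doses.

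What is at stake is how accurately the planned drug exposure table (Table 14.1.7.1 in the SAP list) describes delivered dose.

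**Working it through.** The documents state no RDI value, so there is no figure to reproduce. The check applies the documents' own formulas.

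**Inputs.** Weekly dosing on Days 1, 8, 15 and 22 (Protocol 6.2). Last-dose end date and duration formula (SAP 7.2.1). Withholding rules (Protocol 6.15.2). The 30-100-300 mcg intra-patient escalation (IPE) schedule (SAP Table 1, cohort 7). Assumptions: a fixed weekly dose D unless stated, and a stop decision on the day of the last withheld dose.

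**Step 1: end date.** Let n full doses be given and then m scheduled doses be withheld.

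- To the last dose: RDI = 100 × nD / nD = 100%, whatever m is.
- To the decision: RDI = 100 × n / (n + m).

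| Given | Withheld | To last dose | To decision |
|---|---|---|---|
| 4 | 1 | 100% | 4/5 = 80.0% |
| 4 | 2 | 100% | 4/6 = 66.7% |
| 4 | 3 | 100% | 4/7 = 57.1% |
| 8 | 3 | 100% | 8/11 = 72.7% |
| 12 | 3 | 100% | 12/15 = 80.0% |
| 24 | 3 | 100% | 24/27 = 88.9% |

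Over 1 to 12 doses given and 1 to 4 withheld, the decision-date value runs from 1/5 = 20.0% to 12/13 = 92.3%.

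On the 30-100-300 mcg schedule, with three doses given and three withheld at target, the value to the decision is 430 / (430 + 900) = 32.3%, against 100% to the last dose.

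**Step 2: when 100% does not appear.** Shortfalls before the last dose still count.

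- Two doses given, two held, two given, then three held: 4/6 = 66.7% to the last dose, 4/9 = 44.4% to the decision.
- Two doses at 100 mcg, two reduced to 30 mcg, then three held: 260/400 = 65.0% to the last dose, 260/700 = 37.1% to the decision.

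**Step 3: duration.** For n full weekly doses, last − first + 1 = 7(n − 1) + 1 days. Dose intensity relative to D per week is n / [(7(n − 1) + 1)/7].

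- n = 1: 1/(1/7) = 700%
- n = 4: 4/(22/7) = 127.3%
- n = 8: 8/(50/7) = 112.0%
- n = 24: 24/(162/7) = 103.7%

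With seven days for the final interval the duration is 7n days, and each of these becomes 100%.

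**Step 4: do the two RDI formulas disagree?** That depends on the missing definition. If the planned rate is one dose per seven days, the first formula gives a fully compliant four-dose patient 127% and the second gives 100%. If planned duration is counted by the same 22-day convention, the durations cancel and both give 100%. The SAP does not say which applies.

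**The case against.** The strongest reply is that RDI carries little weight here, and most of that reply stands. Protocol 9.6.2.4 assesses tolerability through interruptions and reductions. SAP 8.6 counts a dose not administered for any reason as an interruption and lists and summarizes the reasons. SAP 8.2.5 tabulates adverse events leading to interruption, reduction or discontinuation, and SAP 5.1 tabulates reasons for stopping. A reader might infer that the withheld doses are lost from reporting; they are absent from one ratio only.

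A reader might also infer that the recommended Phase II dose (RP2D) could be distorted. The documents do not support this. Protocol 6.11 bases that choice on a synthesis of safety, tolerability, pharmacokinetic, pharmacodynamic and activity data without naming RDI. The first report under this SAP is cut off only after the dose has been determined (SAP Section 1).

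Nor does it follow that every patient stopped for toxicity shows 100%, or that the cohorts with most toxicity-related stopping are the most overstated. Earlier omissions and reductions still lower RDI. A patient stopped at once, with no dose withheld first, gets the same value under either end date. The size of the effect depends on withholding before the decision.

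On the formulas, the later bullet can be read as putting the opening text into operation, and Protocol 9.1 leaves reporting detail to the SAP. This weakens any complaint of an undeclared change, but it does not supply the definition of planned duration. Finally, the last-dose date is objective, whereas a decision date depends on when the investigator acts. That is a fair argument for showing both versions.

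**Conclusion.** The point holds as a minor defect in a descriptive summary. The last-dose rule removes withheld terminal doses from the denominator, so a patient whose earlier doses were all given in full can show 100% when the value to the decision is well below that. The gap is 20 to 43 percentage points for four doses given and one to three withheld, and it shrinks as more doses are given. These figures assume fixed weekly dosing and a decision on the day of the last withheld dose. How many patients would follow this pattern cannot be known from the documents.

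The overstatement of mcg/week rests only on the SAP's own duration formula and the weekly schedule. The 127% against 100% conflict in RDI itself is conditional on a planned rate of one dose per seven days. It should be described as an ambiguity, not as a contradiction that the documents establish.

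**What to change.** In SAP 7.2.1:

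- Keep one RDI definition: 100 × total actual dose / total planned regimen dose, including IPE steps, over all scheduled weekly doses from C1D1 to the discontinuation decision or data cut. Count withheld doses as planned but zero.
- Use the same end date for every reason for stopping. A separate rule for progression would make patients non-comparable and would clash with the treatment past progression allowed in Protocol 6.18.
- Optionally show the last-dose version alongside.
- Use (last dose − first dose + 7)/7 weeks as the duration in dose intensity.
- Record the change in SAP Section 12.

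The cost is SAP wording and a small revision of the exposure derivations; the SAP already refers to both dates. Reported RDI will be somewhat lower. Administrative delay before a stop decision may count as missed dosing, and showing both versions makes that visible.
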